5.1.2 Tablet Formulation Introduction, Evaluation, and SMC Decision Making

In addition to the capsule formulation used in this and previous studies, a tablet formulation has been developed. Owing to its formulation characteristics, dissolution of the drug substance may be enhanced in the tablet compared to the capsule formulation. CCI

Physiology-based (GastroPlus) modeling of the human absorption which is predicted to be > 90% at daily doses up to 400 mg, and > 50% at daily doses up to 1000 mg. To take a conservative approach, exposure increases of 2-fold relative to the capsule formulation is assumed.

Currently doses and exposures of up to 200 mg QD of the capsule formulation in combination with RT are considered safe and well tolerated by the SMC. Dose escalation in the current trial is ongoing and the dose of 300 mg is currently being tested. Considering the scenario of an exposure increase of 2-fold of the tablet relative to the capsule formulation a starting dose of 100 mg QD has been selected.

Introduction of the tablet in the Phase Ia part of Arm A

The tablet formulation will be introduced in Phase Ia Arm A of this trial taking into account the available clinical experience and exposure reached after administration of the capsule formulation of M3814 in combination with RT. Subjects will receive the tablet formulation at a starting dose of 100 mg QD on trial days FD 1-5 and FD 7-10. On trial day FD 6, the current capsule formulation will be given as a single dose of 100 mg to allow an intra-individual cross over comparison of single dose PK between the tablet and the capsule formulation. The administration of M3814 formulations will take place 1.5 hours (\pm 30 minutes) before the start of RT. In subsequent dose levels tablet and capsule formulations will always be given using the same dose.

After an initial cohort of 3 patients has been treated at the initial tablet dose of 100 mg, the SMC will decide to treat further patients at this tablet dose with the same dose, or to test optional dose levels (either decreases or increases of dose, the nominal dose will be the same as for the tablets). To decide on the doses to be tested, the SMC will review all available safety, tolerability and PK data, e.g., t_{max} , C_{max} , AUC_{0-24} after single doses of the capsule (FD6) and the tablet (FD1) formulations. The goal is to achieve exposures close to those achieved at the RP2D established for the capsule.

It is foreseen to test up to 6 subjects per tablet dose level.

Introduction of the tablet in other parts of the trial

The Phase Ib part of Arm A may be performed using the M3814 tablet formulation. The first 3 patients of this part will be treated with a dose one dose level below the RP2D determined in the Phase Ia part of Arm A. The SMC will review all available safety, tolerability, and PK data from this cohort and decide on the M3814 dose to be administered to the remaining subjects of this arm.

Based on all available safety, tolerability, and PK data after administration of the tablet in Arm A of the trial, the SMC may decide to change the formulation in the Phase Ia part of Arm B from the capsule to the tablet. This will be done during a dose escalation decision. The selection of the respective tablet dose will take into account the differences in exposure between the capsule and tablet.

The Phase Ib part of Arm B may be conducted using the tablet formulation at the RP2D for the combination with RT and cisplatin identified in the respective Phase Ia part of Arm B.

The ancillary cPoP part of the trial will initially be conducted with the capsule formulation; however, additional cohorts of M3814 (CC1 formulation) may be introduced. The starting dose and subsequent dose levels of M3814 (CC1 formulation) will be defined by the SMC based on PK and safety data generated in ongoing clinical studies evaluating the safety, tolerability, PK, and PD of M3814 (CC1 formulation).

5.2 Discussion of Trial Design

This Phase Ia/Ib, open label trial comprises a dose escalation part (Phase Ia) in which the safety and tolerability of M3814 in combination with RT (and with concurrent cisplatin in Arm B) will be explored in subjects with advanced solid tumors, metastases or lymphomas localized in the head and neck region or thorax (Arm A) and in treatment-naïve subjects with SCCHN (Arm B) to determine MTD and RP2D. The subsequent dose expansion Phase Ib part of the trial will evaluate the safety and explore the efficacy of M3814 in combination with RT in subjects with NSCLC and in combination with CRT (RT and cisplatin) in subjects with SCCHN. In addition, an ancillary cPoP part of the trial will run in parallel with the Phase Ia/Ib parts of the trial to explore the PD of M3814 in combination with RT on target engagement in tumor tissue.

The inclusion and exclusion criteria were chosen to maximize the potential for subject safety and possible benefit from M3814 in combination with RT.

An open label design is considered appropriate for a dose escalation trial with a subsequent expansion cohort in subjects with cancer.

The first cohort of 3 subjects in the Phase Ia, Arm A part of the trial will receive M3814 at a dose of 100 mg and in the Phase Ia, Arm B part of the trial will receive 50 mg, as described in Section 3.3 and Section 3.3.1. Thereafter the trial design for dose escalation employs a Bayesian escalation approach and sequential cohorts of 3 subjects in order to determine the MTD and to enable the SMC to select the next dose from a predicted set of acceptable doses. This design aims to maximize the protection of trial subjects by reducing the number exposed to possible drug

toxicities at each new dose. The SMC may decide to stop dose escalation at any dose level based on safety and PK data.

Introduction and evaluation of the tablet will be performed in the Phase Ia, Arm A part of the trial. A first cohort of patients will receive the tablet formulation at a dose of 100 mg. Based on the previous clinical experience with the M3814 capsule doses up to 400 mg in the ongoing dose escalation, and the anticipated maximal exposure after administration of the tablet, the initial tablet dose of 100 mg in the first tablet cohort is expected to be safe and well-tolerated.

After review of the safety, tolerability, and PK data from this cohort in relation to the data obtained in the ongoing dose escalation, the SMC may decide to test further tablet dose levels. The aim is to confirm the RP2D that has been defined for the capsule, using the tablet formulation.

The design of the tablet testing cohorts in the Phase Ia part of Arm A also includes intra-individual comparison of single dose PK of M3814 after administration of the tablet versus capsule. The capsule administered on FD6 after a 48-hour wash-out is not expected to be influenced by the previous administration of M3814 tablets on FD1 to FD5, considering the median terminal half-life of 5.5 hours (range 2.0 to 8.8 hours, preliminary data estimated in the **CCI** [REDACTED]) after multiple daily dosing. Clinical safety, tolerability, and PK results obtained in Phase Ia Arm A will determine subsequent introduction of the tablet in other parts of the trial.

5.2.1 Inclusion of Special Populations

Not applicable.

5.3 Selection of Trial Population

Only subjects meeting all inclusion criteria and none of the exclusion criteria may be enrolled into the trial. Prior to performing any trial assessments not part of the subject's routine medical care, the Investigator will ensure that the subject has provided written informed consent following the procedure described in Section 9.2.

For subjects in Phase Ia and Ib, archival tumor material must be available, either as a block or slides (most recent material). If no archival material is available then a fresh biopsy should be taken. All subjects in the ancillary cPoP part of the trial must agree to have tumor biopsies collected.

5.3.1 Inclusion Criteria

To be eligible the subject must fulfill all of the following criteria:

1. Subjects must have:
 - a. **Phase Ia part:** advanced solid tumors or metastases including lymphoma localized in the head and neck region or thorax with an indication for fractionated palliative RT (Arm A); or treatment-naïve SCCHN eligible for fractionated curatively intended RT with concurrent cisplatin (Arm B)

b. **Phase Ib part:** treatment-naïve Stage III A/B NSCLC not eligible for surgical resection or concurrent chemoradiation (Arm A expansion cohort) or treatment-naïve SCCHN eligible for fractionated curatively intended RT with concurrent cisplatin (Arm B expansion cohort)

c. **Ancillary cPoP part:** any tumor with at least 2 (sub)cutaneous tumor/metastases at least 2 cm apart which are RT naïve with an indication for high dose palliative RT

2. Measurable or evaluable disease according to Response Evaluation Criteria in Solid Tumors (RECIST) v1.1 (not required for the ancillary cPoP part of the trial)
3. Male or female subjects at least 18 years of age
4. Eastern Cooperative Oncology Group performance status (ECOG PS) ≤ 1
5. Must have read, well understood, and signed and dated the Informed Consent Form (ICF); the subject fully understands the requirements of the trial and is willing to comply with all trial visits and assessments
6. A male participant must agree to use and to have their female partners to use a highly effective contraception (ie, methods with a failure rate of less than 1% per year) as detailed in [Appendix E](#) of this protocol 14 days before first dose of trial treatment, during the treatment period and for at least 90 days after the last dose of trial treatment and refrain from donating sperm during this period
7. A female participant is eligible to participate if she is not pregnant (see [Appendix E](#)), not breastfeeding, and at least one of the following conditions applies:
 - a. Not a woman of childbearing potential (WOCBP) as defined in [Appendix E](#)

OR

 - b. A WOCBP who agrees to use a highly effective contraception (ie, methods with a failure rate of less than 1% per year), as detailed in [Appendix E](#) of this protocol, 14 days before the start of first dose of trial treatment, during the treatment period and for at least 90 days after the last dose of trial treatment
8. Life expectancy of ≥ 3 months (Phase Ia, Arm A) or ≥ 6 months (Phase Ia, Arm B and Phase Ib).

5.3.2 Exclusion Criteria

5.3.2.1 Phase Ia/Ib Parts

Subjects are not eligible for the Phase Ia or Ib parts of the trial if they fulfill any of the following exclusion criteria:

1. Prior treatment consisting of:
 - a. Chemotherapy, immunotherapy, hormonal therapy, biologic therapy, or any other anticancer therapy or IMP within 28 days of first trial drug intake (6 weeks for nitrosoureas or mitomycin C) for Phase Ia, Arm A subjects, and any prior therapy for Phase Ib subjects. For subjects with rapidly growing tumors localized in the head and neck region or thorax where the treating physician cannot wait for 28 days, inclusion may take place if there is no residual toxicity from previous treatment (maximum Common Terminology Criteria for Adverse Events [CTCAE] Grade 1)
 - b. Prior RT to the same region within 12 months (Phase Ia, Arm A; subjects with tumors localized in the head and neck region or thorax) or at any time previously (Phase Ia, Arm B; treatment-naïve subjects with SCCHN and Phase Ib; treatment-naïve subjects with Stage III A/B NSCLC or SCCHN)
 - c. Extensive prior RT on $\geq 30\%$ of bone marrow reserve as judged by the Investigator or prior bone marrow/stem cell transplantation within 5 years before trial start
2. Residual toxicity due to prior therapy with no return to baseline or \leq Grade 1 (except alopecia according to CTCAE v4.03)
3. Surgical intervention, including biopsies and dental root surgeries, within 28 days prior to the first dose of IMP administration or having participated in an interventional clinical trial within 28 days prior to the first dose of IMP administration for Phase Ia/Ib. **Needle biopsies are not considered as surgery.**
4. Poor vital organ functions defined as:
 - a. Bone marrow impairment as evidenced by hemoglobin <10.0 g/dL (5.7 μ mol/L), neutrophil count $<1.0 \times 10^9$ /L, platelets $<100 \times 10^9$ /L
 - b. Renal impairment as evidenced by serum creatinine $>1.5 \times$ upper limit of normal (ULN)
 - c. Liver function abnormality as defined by total bilirubin $>1.5 \times$ ULN or aspartate aminotransferase (AST)/alanine aminotransferase (ALT) $>2.5 \times$ ULN (except for subjects with liver involvement, who can have AST/ALT $>5 \times$ ULN)
5. Significant cardiac conduction abnormalities, including a history of long QTc syndrome and/or pacemaker, or impaired cardiovascular function such as New York Heart Association classification score > 2

6. Hypertension uncontrolled by medication
7. Known CNS metastases unless previously treated by RT, stable by computed tomography (CT) scan for at least 3 months without evidence of cerebral edema and no requirement for corticosteroids or anticonvulsants
8. Known human immunodeficiency virus (HIV) positivity, known clinically significant history of hepatitis (e.g., Hepatitis B [HBV] or Hepatitis C [HCV] virus), current alcohol abuse, or cirrhosis. Screening for HIV to be performed according to local practice and local regulatory guidance. Testing for HIV and HBV/HCV should be repeated if the subject tested negative for the viruses more than 3 months before trial enrollment
9. Ongoing active infection other than HIV, HBV or HCV, or treatment with a live attenuated vaccine within 30 days of dosing
10. History of difficulty swallowing, malabsorption or other chronic gastrointestinal disease or conditions that may hamper compliance and/or absorption of the IMP, current use of percutaneous endoscopic gastrostomy (PEG) tubes
11. History of any other significant medical disease such as major gastric or small bowel surgery, recent drainage of significant volumes (as per Investigator's judgement) of ascites or pleural effusion or a psychiatric condition that might impair the subject's well-being or preclude full participation in the trial
12. Known hypersensitivity to the trial treatment or to one or more of the excipients used
13. Pregnancy or lactation period
14. Legal incapacity or limited legal capacity
15. Subjects currently receiving (or unable to stop using prior to receiving the first dose of trial drug) medications or herbal supplements known to be potent inhibitors of CYP3A or CYP2C19 must stop at least 1 week prior to taking M3814. Subjects receiving potent inducers of CYP3A or CYP2C19 must stop at least 3 weeks prior to taking M3814. Those receiving drugs mainly metabolized by CYP3A with a narrow therapeutic index as judged by the Investigator (and after optional consultation with the Sponsor) must stop at least one day prior to taking M3814.
16. Subjects currently receiving H₂-blocker or proton pump inhibitors (PPIs) (or unable to stop at least 5 days prior to the first treatment).
17. If the planned radiation field includes any part of the esophagus and the subject has symptoms of ongoing esophagitis, the subject is not eligible, unless an esophageal endoscopy rules out the presence of esophagitis.
18. Subjects where more than 10% of the total esophagus volume receives more than 50% of the prescribed RT dose.

Out of range laboratory values may be retested within the timeframe of the screening period.

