- Prior RT to the same region within 12 months (Phase Ia, Arm A; subjects with tumors localized in the head and neck region or thorax) or at any time previously (Phase Ia, Arm B; treatment-naïve subjects with SCCHN and Phase Ib; treatment-naïve subjects with Stage III A/B NSCLC or SCCHN)
- Extensive prior RT on $\geq 30\%$ of bone marrow reserve as judged by the Investigator or prior bone marrow/stem cell transplantation within 5 years before trial start.
- Poor vital organ functions defined as:
 - Bone marrow impairment as evidenced by hemoglobin <10.0 g/dL, neutrophil count $<1.0 \times 10^9/L$, platelets $<100 \times 10^9/L$
 - Renal impairment as evidenced by serum creatinine $>1.5 \times$ upper limit of normal (ULN)
 - Liver function abnormality as defined by total bilirubin $>1.5 \times$ ULN or aspartate aminotransferase (AST)/alanine aminotransferase (ALT) $>2.5 \times$ ULN (except for subjects with liver involvement, who can have AST/ALT $>5 \times$ ULN)
- History of difficulty swallowing, malabsorption or other chronic gastrointestinal disease or conditions that may hamper compliance and/or absorption of the IMP, current use of percutaneous endoscopic gastrostomy (PEG) tubes
- Significant cardiac conduction abnormalities, including a history of long QTc syndrome and/or pacemaker, or impaired cardiovascular function such as New York Heart Association classification score >2 .
- Subjects currently receiving (or unable to stop using prior to receiving the first dose of trial drug) medications or herbal supplements known to be potent inhibitors of cytochrome P450 (CYP)3A or CYP2C19 (must stop at least 1 week prior), potent inducers of CYP3A or CYP2C19 (must stop at least 3 weeks prior), or drugs mainly metabolized by CYP3A with a narrow therapeutic index (must stop at least one day prior).
- Subjects currently receiving H₂-blocker or proton pump inhibitors (or unable to stop at least 5 days prior to the first treatment).
- If the planned radiation field includes any part of the esophagus and the subject has symptoms of ongoing esophagitis, the subject is not eligible, unless an esophageal endoscopy rules out the presence of esophagitis.

- Subjects where more than 10% of the total esophagus volume receives more than 50% of the prescribed RT dose.

Main exclusion criteria for the ancillary cPoP part of the trial

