M3814 will be provided as tablet formulation of 50 mg for oral administration. Dosing schedule of the tablet formulation follows the description given for the capsule formulation above. The tablet formulation will be initially assessed in Phase Ia Arm A taking into account the available safety, tolerability and PK results from the capsule. Standard 3+3 dose escalation design criteria will apply. Comparison of single dose PK data between the tablet and the capsule will guide to define the tablet doses in Phase Ia Arm B and in the Phase Ib parts.

For subjects in Arm B receiving cisplatin:

- There will be no dose escalation of cisplatin above the protocol-specified dose. However, cisplatin dose re-escalation after an initial dose reduction, following the manufacturer's label, is permitted.
- Dose modifications for toxicity should be independently assessed prior to dose administration at each visit following institutional guidelines or [Table 13](#) in the absence of such guidelines.
- Prophylactic granulocyte-colony stimulating factor (G-CSF) may be implemented if neutropenia results in dose reduction or dose delay at prior doses, as suggested in the ASCO guidelines. Therapeutic use of hematopoietic colony-stimulating factors is permitted following ASCO guidelines.
- In the event a subject experiences neutropenia, and G-CSF is initiated, and neutropenia recovers within 48 hours after beginning treatment with G-CSF, G-CSF may be implemented in the management of neutropenia in this subject to avoid dose reductions or holding a dose.

Hemoglobin must be ≥ 10 g/dL at FD 1 and must be ≥ 9 g/dL for all subsequent doses. If hemoglobin is <9 g/dL then appropriate measures according to standard clinical practice must be taken prior to any further dose administration.

Table 13

Dose Modifications for M3814, Radiotherapy, and Cisplatin During the Trial

Toxicity	Dose Modifications		
	M3814 ^a	Radiotherapy ^b	Cisplatin (only for Arm B and in the absence of institutional guidance on cisplatin dose modifications)
Toxicities in Radiation Field Grade 4 
 Mucositis (mucosal inflammation) Radiation dermatitis 	Temporarily interrupt treatment. Resume treatment once severity resolves to Grade \leq 3.	Temporarily interrupt treatment. Resume treatment once severity resolves to Grade \leq 3.	Temporarily interrupt treatment. Resume treatment once severity resolves to Grade \leq 3.

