7.2.7 Clinical Laboratory Tests

Blood samples will be collected locally at screening for clinical laboratory parameter evaluations. These clinical laboratory test results will serve not only as the baseline values for subsequent safety clinical laboratory evaluations during the trial but also as verification that each enrolled subject fulfills all the trial entry criteria and does not meet any of the trial exclusion criteria for laboratory parameters as listed in Section [5.3.2](#). Detailed description of laboratory assessments is provided in Section [7.4.3](#).

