- Failure to collect data necessary to interpret primary endpoints
- Failure to collect necessary key safety data

- Deviations from good clinical practice (e.g. deviations related to informed consent of study participants)
- Other important protocol deviations

All important protocol deviations are documented in SDTM datasets whether identified through site monitoring, medical review or programming.

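### The SI figure beside the 10.0 g/dL hemoglobin limit is wrong in both documents: 10.0 g/dL is about 6.2 mmol/L, and the printed 5.7 mmol/L is about 9.2 g/dL

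*Protocol*

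**What the plan says.** Protocol Section 5.3.2.1, item 4a, which applies to the Phase Ia and Ib parts, reads "Bone marrow impairment as evidenced by hemoglobin <10.0 g/dL (5.7", with the unit after 5.7 printed as micromol/L in the text available. The micro prefix may come from reading the PDF, and nothing below depends on it.

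SAP Appendix 1, PDEV12, defines adequate hematological function for deviation purposes. It requires hemoglobin of at least 10 g/dL and equates that with 5.7 mmol/L.

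Two other places give the limit in g/dL only:

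- The protocol synopsis states the same exclusion as "Bone marrow impairment as evidenced by hemoglobin <10.0 g/dL, neutrophil count", with no SI figure.
- Protocol Section 6.3.1 requires at least 10 "g/dL at FD 1 and must be" at least 9 g/dL for later doses.

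On how the limit is applied, protocol Section 7.2.7 says: "Blood samples will be collected locally at screening for clinical laboratory parameter evaluations". Those results are used to verify eligibility. SAP Section 8.1 says that important deviations are recorded whether "identified through site monitoring, medical review or programming".

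**The concern.** A bracketed SI value in an eligibility criterion serves readers whose laboratory reports in that unit. Here it gives them a different limit from the one beside it. A subject at 9.5 g/dL (about 5.9 mmol/L) is excluded by the g/dL figure but passes a 5.7 mmol/L cutoff.

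Two things could follow. First, a site that reports mmol/L and works from the bracket could enrol subjects below the intended limit. Screening samples are measured locally, and the documents do not say which unit any site reports. Second, PDEV12 carries the same wrong figure, so a check run on its mmol/L value would pass the very subjects that the bracket lets in. SAP Section 15.4 summarises local values after conversion to standard units and lists an SI unit, but does not say whether that unit is mmol/L for hemoglobin.

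**Working it through.** **Inputs**

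- Stated pair: 10.0 g/dL and 5.7 mmol/L (SAP PDEV12; protocol item 4a has the same 5.7).
- Molar mass of hemoglobin: not in the documents, so assumed. Monomer 16.114 g/mmol, range 16.0 to 16.5; tetramer 64.458 g/mmol.

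**Formulas**

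- mmol/L = (g/dL × 10) / molar mass in g/mmol
- g/dL = (mmol/L × molar mass in g/mmol) / 10

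**Attempt to reproduce the plan's figure.** For 10.0 g/dL to equal 5.7 mmol/L, the molar mass would have to be 100 / 5.7 = 17.54 g/mmol. Allowing for rounding of 5.7 (5.65 to 5.75), it would have to lie between 100 / 5.75 = 17.39 and 100 / 5.65 = 17.70. The central value is 17.54 / 16.114 = 1.089 times the monomer mass, about 9% too high, and is nowhere near the tetramer. The figure cannot be reproduced.

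**Conversion in both directions**

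| Basis (g/mmol) | 10.0 g/dL in mmol/L | 5.7 mmol/L in g/dL |
|---|---|---|
| Monomer, 16.0 | 100 / 16.0 = 6.25 | 5.7 × 16.0 / 10 = 9.12 |
| Monomer, 16.114 | 100 / 16.114 = 6.21 | 5.7 × 16.114 / 10 = 9.18 |
| Monomer, 16.125 | 100 / 16.125 = 6.20 | 5.7 × 16.125 / 10 = 9.19 |
| Monomer, 16.5 | 100 / 16.5 = 6.06 | 5.7 × 16.5 / 10 = 9.41 |
| Tetramer, 64.458 | 100 / 64.458 = 1.55 | 5.7 × 64.458 / 10 = 36.7 |

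The tetramer row rules out that basis: it would turn the cutoff into 36.7 g/dL.

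**Size of the shift.** At 16.114 g/mmol, 10.0 − 9.18 = 0.82 g/dL. Allowing for rounding of 5.7, the cutoff lies between 5.65 × 1.6114 = 9.10 and 5.75 × 1.6114 = 9.27 g/dL.

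**If the micro prefix is real.** 5.7 micromol/L = 0.0057 mmol/L, and 0.0057 × 16.114 / 10 = 0.009 g/dL. That cannot serve as a cutoff.

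**Which half of the pair is intended.** The synopsis and the Fraction Day 1 rule in Section 6.3.1 both use 10 g/dL. The g/dL limit is therefore the consistent one, and the error is confined to the SI figure in the two places.

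**The case against.** The conversion itself cannot be defended; the case on the other side concerns the consequence.

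- **Fraction Day 1 rule.** The 10 g/dL requirement in Section 6.3.1 is a separate paragraph in a section headed for both Phase Ia and Phase Ib, and its wording names no arm. Hematology and a re-check of the eligibility criteria are scheduled on Fraction Day 1 in the Phase Ia and Ib schedules (Tables 1 to 6), and Section 7.4.3 requires laboratory results before the first dose. A subject let in by the bracket should meet a second limit, in g/dL only, before dosing. This largely stands. Some doubt remains because the paragraph follows the bullets for Arm B subjects on cisplatin, so its reach to Arm A can be argued either way.
- **Unit in the protocol.** If micromol/L is really printed there, no site could use the figure, and the admission route disappears unless a site silently corrects the unit. That stands as a limit on the harm, but it would make the bracket a worse error, not a lesser one.
- **SAP route.** Nothing says that PDEV12 is programmed or run in mmol/L. SAP Section 10.2.1 builds the listing of eligibility deviations from the Study Entry eCRF page, and PDEV12 itself leads with 10 g/dL. The missed-deviation route is therefore hypothetical. This SAP also covers Phase Ia only.
- **Clinical size.** About 9.2 g/dL is still above the 9 g/dL that the protocol accepts for later doses. That is true, but the entry limit was set higher on purpose, and the bracket contradicts it.

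These points keep the issue minor. None makes 5.7 correct.

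**Conclusion.** The SI value is wrong in protocol item 4a and in SAP PDEV12. The correct equivalent of 10.0 g/dL is about 6.2 mmol/L (6.06 to 6.25 over the monomer masses tried). Read as mmol/L, the printed 5.7 sets a limit about 0.8 g/dL too low. The result rests on one outside input, the molar mass of hemoglobin, and holds for every plausible value of it.

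Confidence is high for the conversion. The consequences are conditional: enrolment below the limit needs a site that reports mmol/L and follows the bracket, and a missed deviation needs a check coded on 5.7. The documents establish neither. This is a minor point, worth correcting because the figure is a decision threshold inside an operative eligibility criterion and is repeated in the matching deviation definition.

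**What to change.** In protocol Section 5.3.2.1, item 4a, and SAP Appendix 1, PDEV12, either delete the SI figure or give the limit as 10.0 g/dL (6.2 mmol/L), and state that g/dL is the governing unit. Deletion is the simpler choice and matches the synopsis. Run any programmed PDEV12 check on g/dL, or on 6.2 mmol/L after unit conversion.

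The cost is one wording correction in each document. No design feature or analysis changes.

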7.4.1.5 Dose Limiting Toxicities

A DLT is defined as any Grade ≥ 3 nonhematologic AE or any Grade ≥ 4 hematologic AE (according to NCI-CTCAE version 4.03) that is related to any of the study treatments and occurs during the DLT period of 5 weeks (Phase Ia, Arm A) or 12 weeks (Phase Ia, Arm B and Phase Ib, first 3 subjects in the expansion cohort of Arm A [NSCLC]) after the first dose of M3814.

A DLT must be confirmed by the SMC.

In addition, the following are considered DLTs:

1. Grade 3 thrombocytopenia with medically concerning bleeding

2. Febrile neutropenia
3. Any toxicity or study treatment-related TEAE that, in the opinion of the SMC, is of potential clinical significance such that further dose escalation would expose subjects to unacceptable risk
4. Any toxicity related to study treatments that causes the subject to receive less than 80% of the planned RT dose
5. Any toxicity related to study treatments leading to an interruption of RT longer than 1 week in Arm B
6. Evidence of study treatment-related hepatocellular injury for more than 3 days, such as > 5 -fold elevations above the ULN of ALT or AST (CTCAE Grade 3 or 4) with or without elevation of serum total bilirubin to $> 2 \times$ ULN, without initial findings of cholestasis (elevated serum alkaline phosphatase) or other apparent clinical causality.

The following study treatment-related AEs are exceptions to the above mentioned DLT definition and are **not** considered to be DLTs:

1. Mucositis (mucosal inflammation), including oral mucositis (stomatitis) of Grade ≥ 3 lasting for ≤ 4 weeks after completion of the study treatments
2. Stomatitis associated toxicities (e.g., swallowing dysfunction [odynophagia, dysphagia], decreased appetite or weight loss due to difficulty or painful swallowing) of Grade ≥ 3 lasting for ≤ 4 weeks after completion of the study treatments
3. Diarrhea of Grade ≥ 3 (≤ 3 days duration) following adequate and optimal therapy
4. Nausea and vomiting of Grade ≥ 3 (≤ 3 days duration) with adequate and optimal therapy
5. Radiation dermatitis and associated toxicities of Grade ≥ 3 lasting for ≤ 4 weeks after completion of the study treatments
6. Neutropenia of Grade 4 lasting for ≤ 5 days and not associated with fever
7. Isolated Grade 4 lymphocytopenia without clinical correlate
8. Fatigue or headache of Grade 3 (≤ 7 days duration) following initiation of adequate supportive care

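### Exclusion 4c, as worded, lets subjects with liver involvement enter with AST/ALT above 5 × ULN and sets no ceiling; the sign should be ≤

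*Protocol*

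**What the plan says.** Protocol Section 5.3.2.1, item 4c, excludes a subject whose total bilirubin exceeds 1.5 × ULN or whose AST or ALT exceeds 2.5 × ULN. It then makes an exception: "except for subjects with liver involvement, who can have AST/ALT $>5 \times$ ULN".

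The synopsis repeats it in its main exclusion criteria, "except for subjects with liver involvement, who can have AST/ALT", followed by the same greater-than sign and the same figure. SAP Appendix 1 carries it again in PDEV13, the deviation code for inadequate liver function.

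The criteria bind as written. Section 5.3 states: "Only subjects meeting all inclusion criteria and none of the exclusion criteria may be enrolled into the trial". Section 7.2.7 uses the screening laboratory results to verify that each enrolled subject "does not meet any of the trial exclusion criteria for laboratory parameters as listed in Section" 5.3.2.

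Elsewhere the protocol treats the same enzyme level as serious toxicity. DLT item 6 in Section 7.4.1.5 refers to more than 5-fold "elevations above the ULN of ALT or AST (CTCAE Grade 3 or 4".

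**The concern.** An exception that relaxes a limit normally sets a higher limit. This one gives permission for values above 5 × ULN and stops there, so subjects with liver involvement have no transaminase ceiling at entry.

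This is an entry-safety criterion in a dose-escalation trial that combines a new agent with radiotherapy. A subject could begin M3814 with transaminases already in the range that the protocol grades 3 or 4. Later liver events in that subject would be hard to attribute, and the rule for restarting M3814 after an interruption would refer back to a Grade 3 or 4 baseline. PDEV13 repeats the wording, so that code would not pick up such an entry.

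**Working it through.** There is no sample-size or power figure to reproduce. The check is a comparison of thresholds and a search for another limit.

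**1. Is the sign an extraction fault?** Unlikely. The same greater-than sign appears in 3 of 3 statements of the criterion, across two documents, and other comparators (<, ≤, ≥) come through correctly in the same protocol section.

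**2. What each reading admits.** Take a subject with liver involvement and bilirubin no higher than 1.5 × ULN.

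| AST/ALT at screening | Literal text | Corrected text (≤5 × ULN) |
|---|---|---|
| 4.8 × ULN | not expressly permitted | admitted |
| 6 × ULN | admitted | excluded |
| 10 × ULN | admitted | excluded |
| 20 × ULN | admitted | excluded |

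The upper entry limit is therefore 2.5 × ULN without liver involvement, none with liver involvement as written, and 5 × ULN with liver involvement after correction. The first row shows that the literal text also fails to state the permission it presumably meant to give, for values between 2.5 and 5 × ULN.

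**3. Does anything else supply a ceiling?**
- Exclusion 2 concerns only "Residual toxicity due to prior therapy with no return to baseline or" Grade 1 or less. It does not reach enzymes raised by tumor in the liver.
- Exclusion 8 covers cirrhosis and clinically significant hepatitis, not an enzyme value.
- Exclusion 11, "History of any other significant medical disease such as major gastric or small bowel surgery" and similar conditions, is a judgement without a numeric AST/ALT limit.
- Section 6.3.1 sets a hemoglobin minimum for dosing. Below 9 g/dL, "then appropriate measures according to standard clinical practice must be taken prior to any further dose administration". It has no corresponding AST/ALT rule.
- The bilirubin limit of 1.5 × ULN still applies, but it does not cap transaminases.

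None of these closes the gap.

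**4. Who is exposed?** The baseline-imaging footnotes in Tables 1 and 2 (Phase Ia Arm A, capsule and tablet) ask for the extent of lesions only. Those in Tables 3 to 6 (Phase Ib Arm A, Phase Ia Arm B, Phase Ib Arm B) also ask for documented M0 stage. Liver involvement is therefore expected essentially in Phase Ia Arm A, which admits metastatic disease.

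**5. What follows for such a subject?**
- DLT item 6 begins above 5 × ULN, so the literal exception starts exactly where the DLT level starts. A cap at 5 × ULN keeps entry values below it.
- Table 13 lets M3814 restart once a non-hematologic toxicity has returned to Grade 1 or less, or to baseline. With a Grade 3 or 4 baseline, M3814 can restart at Grade 3 or 4.
- Under Section 7.4.1.1 a baseline condition that does not worsen is not an adverse event, so the raised baseline value is not itself a DLT.

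**The case against.** The strongest reply is that every other sign in item 4 marks an exclusion trigger: hemoglobin, neutrophils and platelets below a value; creatinine, bilirubin and AST/ALT above one. In that company, >5 × ULN can be read as the replacement trigger for subjects with liver involvement, which already gives a 5 × ULN cap. The literal reading also leaves the range from 2.5 to 5 × ULN without stated permission, which makes little sense. Nothing in the documents shows that a site would admit someone at 10 or 20 × ULN. All of this is fair, but it leads to the same corrected wording. The verb grants permission, and a site or monitor has no text to cite for the cap.

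There are also safeguards that soften the consequences:
- Table 13 requires monitoring at least every 4 days while liver enzymes are Grade 3 or higher, until they recover to Grade 2 or less.
- Arm A chemistry is drawn on fraction days 1, 6 and 10 and during follow-up.
- DLT item 6 requires relation to treatment and no other apparent clinical cause, and the SMC must confirm any DLT.

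These operate after entry and do not replace an entry limit.

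The point about deviations has to be kept narrow. SAP Section 10.2.1 draws its eligibility listing from the study-entry eCRF page, whose wording is not available, and relies on medical review for important deviations. PDEV13 is not flagged as clinically important. The laboratory outputs in SAP Section 15.4 (shift tables from baseline, and a listing of parameters with any Grade 3 or higher value) would show the high baseline. What stands is that neither the criterion nor PDEV13, as written, makes such an entry a deviation.

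**Conclusion.** The criterion is wrong as written and should be corrected. With liver involvement it sets no upper AST/ALT limit, where 5 × ULN was almost certainly meant. The intended cap is an inference, because no passage states it. It rests on the logic of an exception to a 2.5 × ULN limit, on the exclusion-trigger pattern of item 4, and on the DLT level starting above 5 × ULN.

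The practical reach is probably small and cannot be computed, since no count of subjects with liver involvement is given. A subject affected would also need bilirubin no higher than 1.5 × ULN, no cirrhosis or clinically significant hepatitis history, ECOG performance status of 1 or less, and a life expectancy of at least 3 months. No analysis set changes, and no effect on DLT counts is claimed. The case for acting is the safety of entry, at very low cost.

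**What to change.** Replace the greater-than sign before 5 × ULN with ≤ (or write up to 5 × ULN) in protocol Section 5.3.2.1 item 4c, in the synopsis, and in PDEV13 of SAP Appendix 1. DLT item 6 and Table 13 need no change.

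The cost is two wording corrections in the protocol and one in the SAP. A few subjects with liver involvement and AST/ALT above 5 × ULN become ineligible. Any subject already enrolled above 5 × ULN under the present text could be relabeled a deviation by the revised PDEV13, so apply it only to subjects enrolled under the corrected protocol.

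The change does not settle attribution for subjects who enter with raised but permitted enzymes, for example at 4.8 × ULN. Liver events in them will still need SMC judgement.
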